3.3 Product Information

PROCARDIA XL [6]

Nifedipine is a calcium ion influx inhibitor (slow-channel blocker or calcium ion antagonist) and inhibits the transmembrane influx of calcium ions into cardiac muscle and smooth muscle. The contractile processes of cardiac muscle and vascular smooth muscle are dependent upon the movement of extracellular calcium ions into these cells through specific ion channels. Nifedipine selectively inhibits calcium ion influx across the cell membrane of cardiac muscle and vascular smooth muscle without altering serum calcium concentrations. The indications of nifedipine include:

I. Vasospastic Angina

Procardia XL is indicated for the management of vasospastic angina confirmed by any of the following criteria: 1) classical pattern of angina at rest accompanied by ST segment elevation, 2) angina or coronary artery spasm provoked by ergonovine, or 3) angiographically demonstrated coronary artery spasm. In those patients who have had angiography, the presence of significant fixed obstructive disease is not incompatible

with the diagnosis of vasospastic angina, provided that the above criteria are satisfied. Procardia XL may also be used where the clinical presentation suggests a possible vasospastic component, but where vasospasm has not been confirmed, e.g., where pain has a variable threshold on exertion, or in unstable angina where electrocardiographic findings are compatible with intermittent vasospasm, or when angina is refractory to nitrates and/or adequate doses of beta blockers.

II. Chronic Stable Angina (Classical Effort-Associated Angina)

Procardia XL is indicated for the management of chronic stable angina (effort-associated angina) without evidence of vasospasm in patients who remain symptomatic despite adequate doses of beta blockers and/or organic nitrates or who cannot tolerate those agents.

In chronic stable angina (effort-associated angina), nifedipine has been effective in controlled trials of up to eight weeks duration in reducing angina frequency and increasing exercise tolerance, but confirmation of sustained effectiveness and evaluation of long-term safety in these patients is incomplete.

Controlled studies in small numbers of patients suggest concomitant use of nifedipine and beta-blocking agents may be beneficial in patients with chronic stable angina, but available information is not sufficient to predict with confidence the effects of concurrent treatment, especially in patients with compromised left ventricular function or cardiac conduction abnormalities. When introducing such concomitant therapy, care must be taken to monitor blood pressure closely, since severe hypotension can occur from the combined effects of the drugs (See WARNINGS).

III. Hypertension

Procardia XL is indicated for the treatment of hypertension. It may be used alone or in combination with other antihypertensive agents.

Omeprazole/sodium bicarbonate [18]

Omeprazole/sodium bicarbonate is a proton pump inhibitor (PPI) indicated for,

- Short-term treatment of active duodenal ulcer.
- Short-term treatment (4-8 weeks) of active benign gastric ulcer.
- The treatment of heartburn and other symptoms associated with GERD for up to 4 weeks [*Symptomatic GERD*]
- The short-term treatment (4-8 weeks) of erosive esophagitis which has been diagnosed by endoscopy.
- Maintaining healing of erosive esophagitis.
- Capsules 40 mg/1100 mg (omeprazole/sodium bicarbonate) is indicated for the reduction of risk of upper gastrointestinal bleeding in critically ill patients.

Mechanism of Action:

Omeprazole belongs to a class of anti-secretory compounds, the substituted benzimidazoles, that do not exhibit anticholinergic or H₂ histamine antagonistic properties, but that suppress gastric acid secretion by specific inhibition of the H⁺/K⁺ ATPase enzyme system at the secretory surface of the gastric parietal cell. Because this enzyme system is regarded as the acid (proton) pump within the gastric mucosa, omeprazole has been characterized as a gastric acid-pump inhibitor, in that it blocks the final step of acid production. This effect is dose related and leads to inhibition of both basal and stimulated acid secretion irrespective of the stimulus. Animal studies indicate that after rapid disappearance from plasma, omeprazole can be found within the gastric mucosa for a day or more.

Omeprazole is acid labile and thus rapidly degraded by gastric acid. Capsules are immediate-release formulations that contain sodium bicarbonate which raises the gastric pH and thus protects omeprazole from acid degradation.

Pharmacokinetics:

Absorption

In separate *in vivo* bioavailability studies, when omeprazole/sodium bicarbonate Oral Suspension and Capsules are administered on an empty stomach 1 hour prior to a meal, the absorption of omeprazole is rapid, with mean peak plasma levels (% CV) of omeprazole being 1954 ng/mL (33%) and 1526 ng/mL (49%), respectively, and time to peak of approximately 30 minutes (range 10-90 min) after a single-dose or repeated-dose administration. Absolute bioavailability of omeprazole/sodium bicarbonate Powder for Oral Suspension (compared to I.V. administration) is about 30-40% at doses of 20 – 40 mg, due in large part to pre-systemic metabolism.

When omeprazole/sodium bicarbonate Oral Suspension 40 mg/1680 mg was administered in a two-dose loading regimen, the omeprazole AUC (0-inf) (ng·hr/mL) was 1665 after Dose 1 and 3356 after Dose 2, while T_{max} was approximately 30 minutes for both Dose 1 and Dose 2. Following single or repeated once daily dosing, peak plasma concentrations of omeprazole are approximately proportional from 20 to 40 mg doses, but a greater than linear mean AUC (three-fold increase) is observed when doubling the dose to 40 mg. The bioavailability of omeprazole increases upon repeated administration. When omeprazole/sodium bicarbonate is administered 1 hour after a meal, the omeprazole AUC is reduced by approximately 24% relative to administration 1 hour prior to a meal.

Distribution

Omeprazole is bound to plasma proteins. Protein binding is approximately 95%.

Metabolism

Following single-dose oral administration of omeprazole, the majority of the dose (about 77%) is eliminated in urine as at least six metabolites. Two metabolites have been identified as hydroxyomeprazole and the corresponding carboxylic acid. The remainder of the dose was recoverable in feces. This implies a significant biliary excretion of the metabolites of omeprazole. Three metabolites have been identified in plasma – the sulfide and sulfone derivatives of omeprazole, and hydroxyomeprazole. These metabolites have very little or no antisecretory activity.

Excretion

Following single-dose oral administration of omeprazole, little if any, unchanged drug is excreted in urine. The mean plasma omeprazole half-life in healthy subjects is approximately 1 hour (range 0.4 to 3.2 hours) and the total body clearance is 500-600 mL/min.

SMARTPILL™

The SmartPill™ motility testing system is an ingestible capsule that offers a convenient and radiation-free way to assess motility by measuring pressure, pH, and temperature throughout the entire gastrointestinal (GI) tract for patients with unexplained GI symptoms, such as nausea, bloating, constipation, abdominal pain, and vomiting. As it moves through the GI tract, it wirelessly and continuously transmits data to a recorder worn on the belt or lanyard for up to 5 days or when it passes with a regular bowel movement.

In the current study, the SmartPill™ will be used to measure subjects' gastric pH conditions (over a period of 8 hours) under which the nifedipine and co-administered nifedipine and omeprazole/sodium bicarbonate is released in vivo. This direct measurement of gastric pH will confirm a positive pharmacologic response (i.e. increased gastric pH) to proton pump inhibitors in healthy volunteers and determine the extent of gastric pH elevation as a result of 7-day multiple-dose of omeprazole/sodium bicarbonate capsules. In contrast with conventional gastric or nasogastric intubation methods, subjects should feel significantly less pain or discomfort when swallowing the capsule or while the capsule moves through the GI tract. It is naturally passed during a bowel movement, usually within a few days.

SmartPill™ uses MotiliGI® software to display and analyze the data, providing test results in both graphical and report formats. SmartPill™ provides valuable diagnostic information including:

- Gastric emptying time

- Small bowel transit time
- Colonic transit time
- Whole gut transit time
- Pressure patterns from the antrum and duodenum

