2.0 TABLE OF STUDY PROCEDURES

Procedure/Activity	Time points						
	Screening	Each Period Check-in	Period 1	Period 2	Period 3	Period 4	Post-Study
ICF	X ^a						
Drugs of Abuse	X	X					
Alcohol Test	X	X					
Cotinine	X	X					
Pregnancy (hCG) Test*	X	X					
Vital Signs (BP, HR, RR and Temperature)	X		X ^b	X ^b	X ^b	X ^b	X
Laboratory Testing	X	X [#]					X
Medical History	X						
BMI	X						
ECG	X						
Inclusion/Exclusion Assessment	X						
Restrictions Compliance Check		X	X	X	X	X	
Physical Exam	X						X
SmartPill™ Administration			X ^c	X ^c	X ^c	X ^c	
Nifedipine ER tablets Dosing (Test)			X ^d		X ^d		
PROCARDIA XL (Ref)				X ^d		X ^d	
omeprazole/sodium bicarbonate capsules Dosing					X ^e	X ^e	
pH Measurement			X ^f	X ^f	X ^f	X ^f	
PK Sampling			X ^g	X ^g	X ^g	X ^g	
Adverse Event Reporting		X ^h	X	X	X	X	X
Meals		X	X ⁱ	X ⁱ	X ⁱ	X ⁱ	

- # Laboratory testing (hematology, serum biochemistry, and urine analysis) at each period check-in for Study arm A and B on Day 1 and for Study arm C and D it will be done at check-in on Day 3.
- a- At screening and prior to any medical screening procedures.
- b- Vital signs measurements (BP, HR, RR and temperature) to be obtained for Study arm A and B, and on Day 7 for Study arm C and D at pre-dose and at 4, 12 and 24 hours after dosing nifedipine ER tablets in each study period, and at pre-dose and 1 hour after omeprazole/sodium bicarbonate capsules daily dosing (Day 1 to Day 6) in each study period for Study arm C and D.
- c- SmartPill™ capsules will be administered 30 minutes before dosing nifedipine ER tablets (Study arm A and B), and 30 minutes before dosing nifedipine ER tablets and omeprazole/sodium bicarbonate capsules (Study arm C and D) on Day 7.
- d- Study arm A and B: Nifedipine dosing on Day 2 in each study period
Study arm C and D: Nifedipine dosing on Day 7 co-administered with omeprazole/ sodium bicarbonate in each study period.
- e- Study arm C and D: omeprazole/ sodium bicarbonate capsules dosing for 7 days (Day 1 to 7) in each study period.
- f- pH will be measured at 0, 1, 2, 3, 4, 5, 6, 7, and 8 hours after SmartPill™ administration in each study period.
- g- PK sampling - Pre-dose (0 hour) and at 1, 2, 3, 4, 5, 6, 7, 8, 9, 10, 12, 16, 20, 24, 36, and 48 hours after nifedipine dosing in each study period.
- h- Pre-dose conditions at Period 1 check-in.
- i- Study arm A and B: Meals will be served at approximately 6.5, 10.5, 14.0, 24.5, 28.5, 33.5 and 37.5 hours after dosing.

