13.3.2 Pharmacodynamic Analysis

Pharmacodynamic (PD) parameters of omeprazole/sodium bicarbonate (i.e. proton pump inhibitors) will be evaluated for all subjects with at least 4 hours pH measurement. The PD parameters include gastric pH, change of gastric pH from baseline.

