 - H01: There is no difference between Study Arm A and Study Arm C
 - H11: There is a difference between Study Arm A and Study Arm C
- For the comparison of Study Arm D and Study Arm B
 - H02: There is no difference between Study Arm D and Study Arm B
 - H12: There is a difference between Study Arm D and Study Arm B
- For the comparison of Study Arm A and Study Arm B
 - H03: There is no difference for the change of median between Study Arm A and Study Arm B
 - H13: There is a difference for the change of median between Study Arm A and Study Arm B

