B	19	Yes	8:00 PM	Arrive in the evening to check-in for check-in procedure
	20	Yes	(1) 7:00 AM (2) 7:30 AM (3) 7:30 AM →	(1) Administer SmartPill (2) Administer study drug brand-name nifedipine extended release tablets (3) Draw blood
	21	Yes	Throughout the day	Draw blood
	22	No	→ 7:30 AM	After the last time point of blood draw, you will be released from the clinical site
	23 to 36	No		Washout period (break), at least 14 days
C	37	No	(1) 6:30 AM (2) 7:30 AM (3) 8:30 AM	(1) Arrive in the clinic (2) Omeprazole/sodium bicarbonate administration (3) Released from the clinic
	38	No	(1) 6:30 AM (2) 7:30 AM (3) 8:30 AM	(1) Arrive in the clinic (2) Omeprazole/sodium bicarbonate administration (3) Released from the clinic
	39	Yes	(1) 6:30 AM (2) 7:30 AM (3) Afternoon	(1) Arrive in the clinic to check-in (2) Omeprazole/sodium bicarbonate administration (3) Check-in procedure
	40	Yes	7:30 AM	Omeprazole/sodium bicarbonate administration
	41	Yes	7:30 AM	Omeprazole/sodium bicarbonate administration
	42	Yes	7:30 AM	Omeprazole/sodium bicarbonate administration
	43	Yes	(1) 7:00 AM (2) 7:30 AM (3) 7:30 AM –	(1) Administer SmartPill (2) Administer Omeprazole/sodium bicarbonate and study drug generic nifedipine extended-release tablets (3) Draw blood

	44	Yes	Throughout the day	Draw blood
	45	No	7:30 AM	After the last time point of blood draw, you will be released from the clinical site
	46 to 59	No		Washout period (break), at least 14 days
D	60	No	(1) 6:30 AM (2) 7:30 AM (3) 8:30 AM	(1) Arrive in the clinic (2) Omeprazole/sodium bicarbonate administration (3) Released from the clinic
	61	No	(1) 6:30 AM (2) 7:30 AM (3) 8:30 AM	(1) Arrive in the clinic (2) Omeprazole/sodium bicarbonate administration (3) Released from the clinic
	62	Yes	(1) 7:00 AM (2) 7:30 AM (3) Afternoon	(1) Arrive in the morning to check-in (2) Omeprazole/sodium bicarbonate administration (3) Check-in procedure
	63	Yes	7:30 AM	Omeprazole/sodium bicarbonate administration
	64	Yes	7:30 AM	Omeprazole/sodium bicarbonate administration
	65	Yes	7:30 AM	Omeprazole/sodium bicarbonate administration
	66	Yes	(1) 7:00 AM (2) 7:30 AM (3) 7:30 AM –	(1) Administer SmartPill (2) Administer Omeprazole/sodium bicarbonate and study drug brand-name nifedipine extended-release tablets (3) Draw blood
	67	Yes	Throughout the day	Draw blood
	68	No	7:30 AM	After the last time point of blood draw, you will be released from the clinical site

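### The planned pH contrasts measure the PPI/antacid combination and cannot by themselves confirm a response to omeprazole

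*Combined protocol and SAP*

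**What the plan says.** Section 3.3 (SmartPill) gives the pH record two jobs. One is to describe the gastric conditions in which nifedipine is released. The other is confirmatory: "This direct measurement of gastric pH will confirm a positive pharmacologic response (i.e. increased gastric pH) to proton pump inhibitors", and to "determine the extent of gastric pH elevation as a result of 7-day multiple-dose of omeprazole/sodium bicarbonate capsules". The only criterion given for a response is a rise in pH.

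For the capsule, Section 3.3 (Mechanism of Action) says it contains "sodium bicarbonate which raises the gastric pH and thus protects omeprazole from acid degradation".

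For timing, footnote c of Section 2.0 places the SmartPill "30 minutes before dosing nifedipine ER tablets and omeprazole/sodium bicarbonate capsules (Study arm C and D) on Day 7". Footnote f reads: "pH will be measured at 0, 1, 2, 3, 4, 5, 6, 7, and 8 hours after SmartPill™ administration in each study period". The example schedule in Appendix A agrees, with the SmartPill at 7:00 AM and, at 7:30 AM, "Administer Omeprazole/sodium bicarbonate and study drug generic nifedipine extended-release tablets".

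For analysis, Section 13.3.2 begins: "Pharmacodynamic (PD) parameters of omeprazole/sodium bicarbonate (i.e. proton pump inhibitors) will be evaluated for all subjects". Section 13.3.3 plans an ANOVA of gastric pH and of its change from baseline, with contrasts C minus A and D minus B. The first null hypothesis is "H01: There is no difference between Study Arm A and Study Arm C", and the second is the same for D and B. No summary measure over time, time window, baseline or response threshold is defined. Under Section 13.2, readings up to 4 hours are enough to enter the PD analysis set.

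**The concern.** Two components of the capsule can raise gastric pH: omeprazole, through acid suppression built up over daily dosing, and sodium bicarbonate, through direct neutralisation after each dose. Arms A and B receive neither. No arm gives one component without the other, and the analysis plan does not separate them by time. A rise in pH on Day 7 satisfies the criterion in Section 3.3 whichever component caused it.

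At stake is one conclusion: that these volunteers responded to the PPI. The rationale in the Synopsis looks towards people taking a PPI or with abnormal gastric pH. For that use, it matters whether the stomach was already less acidic before the Day 7 dose or became so only after the antacid. As written, the plan would report the PPI response as confirmed in either case.

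**Working it through.** The plan states no figure on this point, so there is none to reproduce. The check is one of timing, followed by an illustration under assumed values.

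**1. Reading times relative to the Day 7 capsule.** Inputs: readings at 0 to 8 h after the SmartPill (Section 2.0, footnote f) and a 0.5 h lag to the capsule (footnote c). Time from capsule = time from SmartPill − 0.5 h.

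| After SmartPill (h) | 0 | 1 | 2 | 3 | 4 | 5 | 6 | 7 | 8 |
|---|---|---|---|---|---|---|---|---|---|
| From capsule (h) | −0.5 | 0.5 | 1.5 | 2.5 | 3.5 | 4.5 | 5.5 | 6.5 | 7.5 |

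Eight of nine readings follow the bicarbonate dose and one precedes it. In the minimum record accepted by Section 13.2 (0 to 4 h), four of five follow it. The first Day 7 meal is at about 6.5 h after dosing (Section 8.2). The 7 h reading therefore falls at about mealtime, and the 8 h reading is not fasting.

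**2. What each contrast contains.** Let P0 be the omeprazole effect carried into Day 7 from Days 1 to 6, P1 the omeprazole effect at a later reading, and B the effect of the Day 7 bicarbonate at that reading.

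- Pre-dose reading, C − A: P0.
- Post-dose reading, C − A: P1 + B.
- Change from a same-day 0 h baseline, C − A: (P1 + B) − P0. If the carried-over effect simply persists (P1 = P0), this equals B.

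So if baseline means the same-day 0 h reading, the change score removes the effect of the six prior days and leaves only the acute Day 7 effect. The plan does not say which baseline it means.

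**3. Could the antacid alone give a significant result?** Assumptions, none of them in the documents: omeprazole effect zero, scheduled readings averaged within a period, and within-subject SD of that average 0.5, 1.0 or 1.5 pH units (the same for both averages). Inputs from the plan: 52 completers (Section 7.1) and two-sided alpha 0.05 (Section 13.3.3).

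Shift = (readings lifted × lift) / (readings averaged). SE = SD × √(2/52), which is 0.196 at SD 1.0. Probability of a significant rise ≈ Φ(shift/SE − 1.96).

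| Assumed bicarbonate lift | Average of | Shift | SD 0.5 | SD 1.0 | SD 1.5 |
|---|---|---|---|---|---|
| 2 units on the first two post-dose readings | 0–8 h (9) | 2×2/9 = 0.44 | 0.99 | 0.62 | 0.33 |
| 2 units on the first two post-dose readings | 0–4 h (5) | 2×2/5 = 0.80 | 1.00 | 0.98 | 0.78 |
| 1 unit on one reading | 0–8 h (9) | 1×1/9 = 0.11 | 0.20 | 0.08 | 0.06 |
| 1 unit on one reading | 0–4 h (5) | 1×1/5 = 0.20 | 0.53 | 0.17 | 0.10 |

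The result runs from barely detectable to near certain, and the documents contain nothing that narrows it.

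**The case against.** The strongest reply is that the combination is the declared intervention. The Synopsis and Sections 4.1, 5.1 and 5.3 call it PPI/antacid, and Section 3.3 introduces the combined product as a PPI. The second half of the Section 3.3 sentence concerns the capsules, not omeprazole alone. The null hypotheses say only that the arms do not differ, so the tests are valid for the combination. Post-dose readings are also what is needed to describe pH while nifedipine is being released. All of this stands, and it is why the planned tests should stay. It does not rescue the attribution to proton pump inhibitors in Sections 3.3 and 13.3.2. Section 3.1 itself lists PPIs and PPIs with antacids separately.

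A second reply is that a zero omeprazole effect is implausible. Section 3.2 says seven-day PPI dosing effectively raises gastric pH, and Sections 8.3 and 5.2 provide for dosing in the clinic with mouth checks. That is fair as a prior expectation. But a measurement meant to confirm the response cannot take it for granted.

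Third, the pre-dose window has its own weaknesses. The SmartPill is taken with 8 fl. oz. of water and up to 24 in total (Section 8.3), which may dilute acid in every arm and shrink the contrast. The window also falls about 23.5 h after the Day 6 capsule, at the end of the dosing interval. This stands, and it is a reason to add the contrast as supportive rather than move the planned tests onto it.

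A reader might also infer that eight of the nine readings are contaminated. The documents do not support that. Eight of nine is a count of timing. No duration of bicarbonate action is given, and later readings may be little affected.

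**Conclusion.** The concern holds as a limit on interpretation. A significant C − A or D − B difference in pH establishes an effect of the PPI/antacid combination. It could arise partly or wholly from the Day 7 antacid, so alone it does not confirm acid suppression from the six prior days of omeprazole. The timing count (8 of 9 readings, or 4 of 5 in the minimum record), the absence of bicarbonate in arms A and B, and the direction of its effect all come from the documents. The probabilities do not: they rest on assumed lifts, durations, SDs and a simple average.

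Two stronger readings are tempting. One is that the contrast would be positive even if omeprazole had done nothing. The illustration supports only that it could be. The other is that the PK verdicts are undermined. They are not: no PK comparison or analysis-set rule in Sections 13.1 and 13.3.3 depends on the pH result, and the four PK ratios remain valid for the combined product.

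**What to change.** In Sections 13.3.2 and 13.3.3:

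- Keep the planned C − A and D − B tests, labelled as the effect of the PPI/antacid combination on pH during nifedipine release.
- Prespecify a supportive C − A and D − B contrast on the pre-dose record (the 0 h reading and the continuous trace up to capsule dosing on Day 7), against the same pre-dose window in A and B. Present this as the evidence for the PPI response.
- Show later fasting gastric readings by time after capsule dosing, without treating any cut-off as the end of the bicarbonate effect.
- Define baseline, and state that change from the same-day Day 7 0 h reading is not used for the PPI response.
- Reword Sections 3.3 and 13.3.2 to match. Section 8.4 should say that the continuous record starts at SmartPill ingestion, since it now refers only to 24 hours post-dose.

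The cost is wording and one extra table, with no new procedure. The drawback is that the pre-dose window is about 30 minutes long, noisy, affected by the SmartPill water and representative of the end of the dosing interval. It also assumes that the Day 6 bicarbonate no longer acts about 23.5 h later. A weak result there would not by itself show that omeprazole failed.

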4.0 STUDY OBJECTIVE

4.1 Study Objective

The objective of this study is to compare pharmacokinetics of nifedipine from both generic Nifedipine oral extended-release tablets, 60 mg and reference listed drug PROCARDIA XL (nifedipine) extended-release tablets, 60 mg when co-administered with or without proton pump inhibitor (PPI)/antacid, omeprazole/sodium bicarbonate capsules 40 mg/1100 mg capsules in healthy males and non-pregnant females under fasting conditions.

The two one-sided t-tests procedure Schuirmann proposed will be used to construct the 90% confidence interval at the $\alpha=0.05$ level of significance for the ratio of geometric mean of PK parameters AUC_t, AUC_{inf} and C_{max}. The limits of the 90% confidence intervals are 80.00%-125.00% which will be used for the statistical hypothesis testing. Therefore, it consists of decomposing the interval hypotheses into two sets of one-sided hypotheses.

For the drug interaction for both test and reference products, the calculated 90% confidence interval (CI) for the ratios of geometric means for AUC_t, AUC_{inf} and C_{max} will be used for the following two PK comparisons to assess if the statistical significance of interaction effect between the product type effect (test or reference) and the effect of co-administrating PPI/antacid is or not.

- Test with PPI (Study Arm C)/Test without PPI (Study Arm A)
- Reference with PPI (Study Arm D)/Reference without PPI (Study Arm B)

Hypothesis 1.1: The hypotheses for testing of the interaction effect between Test product and the effect of co-administrating PPI/antacid are as follows:

- The null hypothesis (H01): there is statistical significance of the interaction effect if the 90% CI of the ratios of geometric means for AUC_t, AUC_{inf} and C_{max} is less than 80.00%.
- The alternative hypothesis (H11): there is no statistical significance of the interaction effect if the 90% CI of the ratios of geometric means for AUC_t, AUC_{inf} and C_{max} is greater than or equal to 80.00%.
- The null hypothesis (H02): there is statistical significance of the interaction effect if the 90% CI of the ratios of geometric means for AUC_t, AUC_{inf} and C_{max} is greater than 125.00%.

- The alternative hypothesis (H12): there is no statistical significance of the interaction effect if the 90% CI of the ratios of geometric means for AUC_t, AUC_{inf} and C_{max} is less than or equal to 125.00%.

Hypothesis 1.2: The hypotheses for testing of the interaction effect between Reference product and the effect of co-administrating PPI/antacid are as follows:

- The null hypothesis (H03): there is statistical significance of the interaction effect if the 90% CI of the ratios of geometric means for AUC_t, AUC_{inf} and C_{max} is less than 80.00%.
- The alternative hypothesis (H13): there is no statistical significance of the interaction effect if the 90% CI of the ratios of geometric means for AUC_t, AUC_{inf} and C_{max} is greater than or equal to 80.00%.
- The null hypothesis (H04): there is statistical significance of the interaction effect if the 90% CI of the ratios of geometric means for AUC_t, AUC_{inf} and C_{max} is greater than 125.00%.
- The alternative hypothesis (H14): there is no statistical significance of the interaction effect if the 90% CI of the ratios of geometric means for AUC_t, AUC_{inf} and C_{max} is less than or equal to 125.00%.

For the relative bioavailability between test and reference products under different conditions (with or without PPI), the calculated 90% confidence interval (CI) for the ratios of geometric means for AUC_t, AUC_{inf} and C_{max} will be used for the following two PK comparisons to assess if the relative bioavailability is or not.

- Test with PPI (Study Arm C)/Reference with PPI (Study Arm D)
- Test without PPI (Study Arm A)/Reference without PPI (Study Arm B) →
Although the generic applicant has already confirmed the bioequivalence between Test and Reference in the absence of PPI, this study will confirm this result.

Hypothesis 2.1: The hypotheses for the assessment of relative bioavailability for Test product with and without PPI are as follows:

- The null hypothesis (H01): there is no comparable bioavailability if the 90% CI of the ratios of geometric means for AUC_t, AUC_{inf} and C_{max} is less than 80.00%.
- The alternative hypothesis (H11): there is comparable bioavailability if the 90% CI of the ratios of geometric means for AUC_t, AUC_{inf} and C_{max} is greater than or equal to 80.00%.
- The null hypothesis (H02): there is no comparable bioavailability if the 90% CI of the ratios of geometric means for AUC_t, AUC_{inf} and C_{max} is greater than 125.00%.

- The alternative hypothesis (H12): there is comparable bioavailability if the 90% CI of the ratios of geometric means for AUC_t, AUC_{inf} and C_{max} is less than or equal to 125.00%.

Hypothesis 2.2: The hypotheses for the assessment of relative bioavailability for Reference product with and without PPI are as follows:

- The null hypothesis (H03): there is no comparable bioavailability if the 90% CI of the ratios of geometric means for AUC_t, AUC_{inf} and C_{max} is less than 80.00%.
- The alternative hypothesis (H13): there is comparable bioavailability if the 90% CI of the ratios of geometric means for AUC_t, AUC_{inf} and C_{max} is greater than or equal to 80.00%.
- The null hypothesis (H04): there is no comparable bioavailability if the 90% CI of the ratios of geometric means for AUC_t, AUC_{inf} and C_{max} is greater than 125.00%.
- The alternative hypothesis (H14): there is comparable bioavailability if the 90% CI of the ratios of geometric means for AUC_t, AUC_{inf} and C_{max} is less than or equal to 125.00%.

